5.1.1.2. Treatment dose during primary treatment period and maintenance period

After completing dose adjustment at Visit 9, each patient will receive an optimized dosage of baricitinib that was determined throughout the dose adjustment period. Patients should maintain their optimized baricitinib dosage during the primary and maintenance treatment periods as much as possible.

5.1.1.3. Dose modification during treatment period

In any of following dose modification, the reason for dose modification will be documented in the medical record.

Weight changes:

If the patient's weight changes during the study and requires a change in the dosing regimens as outlined in [Table JAJE.5](#), the dose may be adjusted to meet the dosing regimen based on current weight.

- If a patient gains weight during the study and the increase in weight results in a change in weight range, the investigator may opt to increase the dose based on the patient's new weight range. The investigator should ensure that the increase in weight is not related to fluid retention.
- If the patient loses weight during the study, the investigator may opt to keep the patient on their current dose.

Dose reduction or increase:

Dose modification may be allowed if needed for appropriate medical management. In case of dose modification, the investigator must notify Lilly or its designee as soon as possible.

- **Dose reduction by safety concern**

In the event of AEs possibly attributable to the study drug, the dose may need to be reduced. Dose reductions, interruptions, or discontinuations may also occur based on review of the patient's clinical and pharmacokinetic (PK) data (if available). Except in cases of emergency, it is recommended that the investigator consult with Lilly or its designee before interrupting or discontinuing therapy. The investigator must obtain approval from Lilly or its designee before restarting.

- **Dose increase by continuous inadequate response after dose adjustment period**

If a patient continues to have an inadequate response to the baricitinib dose as evidenced by an elevated diary score or ongoing clinical disease activity reflected by increased symptoms or elevated markers of inflammation, the dose may be increased in the dose escalation steps shown in [Table JAJE.5](#). When patients have their dose escalated, they must receive an escalated dose for at least 72 hours from last dose.

If a patient reaches the maximum total daily dose as specified in ([Table JAJE.5](#)) and has an inadequate response to treatment, the patient may be discontinued from the study to pursue other treatment options. However, if the investigator determines that it is in the best interest of the patient to continue treatment, the patient may continue in the study. This will not be considered a protocol violation.

5.1.1.4. Pharmacokinetic Sampling

Blood samples will be collected to determine baricitinib concentrations. Samples will be collected according to the Section 9.5.

5.1.2. Patient Diary and Diary Score

Patient diaries will be provided for daily collection of information regarding the patient's signs and symptoms. Diaries are specific to individual indications or conditions (ie, NNS/CANDLE, SAVI, or AGS). The patient diaries are shown in Section 9.1.1. Each patient (or caregiver) will complete the diary at approximately the same time every day during the screening period and for the duration of the study. Ideally, the same person will complete the diary each day. It will not be considered a protocol violation even if record time or assessor for the diary is different.

Patients with NNS/CANDLE or SAVI:

For patients with NNS/CANDLE or SAVI, the patient or caregiver will be instructed to rate each symptom (fever, rash, musculoskeletal pain, and fatigue [all diaries], headache [NNS/CANDLE diary only], respiratory/breathing problems, and ulcers/ischemic lesions [SAVI diary only]) in the diary on a scale from 0 to 4 (where a score of 0 = no symptoms, 1 = mild symptoms, 2 = moderate symptoms, 3 = more severe symptoms, and 4 = severe symptoms [equivalent to “worst” symptoms])(See Section 9.1.1.1 and 9.1.1.2).

Importantly, these ratings should evaluate the *impact* of each symptom on the patient, and not the severity of the symptom itself. For example, to assess the symptom of fever, the patient or their caregiver should assess the impact fever has on the patient, regardless of whether the actual temperature of the patient is known. If no fever is apparent and the patient does not have any limitations on daily activities, the fever score for that day would be 0. If the patient has a transient fever that minimally impacts daily activities, the fever score for that day would be 1, and so on. A fever score of 4 would indicate that the patient has a fever with high impact on the patient, for example, being bedridden.

Patients with AGS:

For patients with AGS, the patient (or caregiver) will be instructed to rate each symptom (neurologic disability, crying, length of uninterrupted sleep, generalized seizure, fever, excessive irritability, skin findings [body], and skin findings [hands, feet, and ears]) as defined in the diary (See section 9.1.1.3).

The diary is to be completed daily throughout the study. The diary score is used to confirm patient eligibility, assess disease activity and inform the need for an additional dose increase (up to the maximum allowed dose as detailed in Table JAJE.5) or initiation of steroid weaning (if the patient is receiving steroids) as described in the section 5.1.1. At required visits, site personnel will calculate the average score for each symptom being collected on the diary (that is, the average of 7 days prior to the visit, correcting for any day for which diary scores were not

recorded). The site personnel will take the average scores for each symptom, sum them, and divide by the number of assessed symptoms to calculate the average diary score for a patient.

The investigator should review the entire diary and average diary scores at required visits. If there is a trend in the diary scores, (ie, initial high scores resolve by the end of the diary period or lower scores become higher by the end of the diary period), the investigator has the option of escalating or not escalating the patient's dose of baricitinib.

Method of calculation for the average diary score by site personnel:

The average diary score is calculated as follows:

- Average score of each symptom is calculated using data from 7 days preceding the current visit (not including data on the day of current visit).
- The calculated average score for each symptom is summed up and divided by the number of assessed symptoms (ie, 5 symptoms for NNS/CANDLE, 6 symptoms for SAVI, or 8 symptoms for AGS) to calculate the average score for each patient.

Site personnel will be required to calculate the average score at least for eligibility (Visit 2, Visit 6) and dose adjustment (Visit 7, 8, 9). The calculation may be performed at any time during the study if necessary in the opinion of the investigator. The calculated average score will be documented in the source document.

5.2. Number of Patients

Because the medical conditions being treated in the study are very rare in Japan, it is anticipated that relatively few patients will be enrolled. Approximately 5 patients will be enrolled. The sponsor will try to enroll more than 1 patient per disease.

However, given the scarcity of patient population for each of these target diseases in Japan, it may be possible that the study is completed without enrolling any patient for a specific disease if no eligible patient could be found.

5.3. End of Study Definition

End of the study is the date of the last visit or last scheduled procedure shown in the Schedule of Activities (Section 2) for the last patient.

5.4. Scientific Rationale for Study Design

This study is a Phase 2/3, multicenter, open-label, single-arm design intended to provide baricitinib to patients with NNS/CANDLE, SAVI, or AGS. Patients will receive an initial dose that may be escalated using dose escalation tables to an effective and tolerable dose during the dose adjustment period. Patients should maintain their optimized baricitinib dosage during the primary treatment period and the maintenance treatment period.

Continued ongoing inflammation causes organ damage and results in significant morbidity and mortality. There are no approved drugs for NNS/CANDLE, SAVI, or AGS in Japan or anywhere else in the world. Many patients require high dose corticosteroids to control systemic

symptoms. However, the chronic high doses of steroids frequently required for treatment further contributes to the morbidity and mortality associated with these syndromes. Given the serious and life-threatening nature of these syndromes, no standard of care, and unsustainable chronic doses of steroids, an open-label study is deemed appropriate.

5.5. Justification for Dose

Patients will receive an initial dose based on weight class and eGFR and may have their dose escalated to determine a tolerable dose. Dose escalation according to [Table JAJE.5](#) will be performed up to the maximum allowable dose level, as long as there are no safety concerns that would preclude increasing the dose.

Initial dose escalation parameters were supported by PK results following baricitinib treatment of the first 2 CANDLE patients in Study JAGA as well as results from a Phase 2b study in RA patients. Improvements in patients with RA, including significant improvement in American College of Rheumatology responses, were achieved at a dose of 4 mg which approximates a dose of 0.05 mg/kg. In the first 2 CANDLE patients in Study JAGA, initial improvements in clinical status were only observed upon achieving a stable daily dose of 2 mg approximating a 0.1 mg/kg dose. The requirement for a higher dose to achieve efficacy is likely due to 2 distinct reasons. The first reason is the nature of the diseases that results from auto-inflammatory syndromes appears to require higher concentrations of disease-modifying anti-rheumatic drugs (Goldbach-Mansky et al. 2006) for adequate disease management. The second reason is based on the generally shorter half-life of baricitinib observed in CANDLE patients in Study JAGA that requires higher mg/kg dosing in order to achieve therapeutic exposures.

With a 1 mg dose, the assumed maximal concentration at 1.5 hours is between 10 and 40 nM based on the first 2 patients. With whole blood half maximal inhibitory concentration (IC_{50}) values for inhibition of IL-6 induced STAT-3 phosphorylation of 104 ± 14 nM (n=5) (Baricitinib Investigator's Brochure) exposure data would suggest that the dose will need to be greater than 2 mg (or 0.1 mg/kg) to approach therapeutic levels.

As baricitinib PK information and the associated clinical response in the JAGA CANDLE and SAVI patient population became available, the dose-escalation- scheme was modified accordingly (Kim et al. 2018). Based on observed dose titration and stable dose in the 18 JAGA patients seen at the National Institutes of Health up to 04 March 2016 and the PK analyses from these patients (Kim et al. 2018) in JAGA, cut off values of 20 kg and 40 kg for weight and of 120 mL/min/1.73 m² for eGFR were used for dose adjustment and are reflected in the JAGA protocol amendments.

In the updated population PK analysis which was recently available, baricitinib PK were further characterized with plasma concentration data available from 71 patients in JAGA. Overall, the mean AUC over 24 hours at steady state ($AUC_{0-24,ss}$) for all JAGA patients taking baricitinib doses of 3-12 mg daily was 896 ng*h/mL (90% CI = 473-1490 ng*h/mL). The mean $AUC_{0-24,ss}$ is 1.9-fold greater than the mean baricitinib exposures in adult patients with RA receiving doses of 4 mg once daily.

The analysis confirmed renal function estimated by eGFR as a significant covariate on CL/F. Due to the minimum effect size characterized of eGFR on AUC and C_{max} in the eGFR range greater than 60 mL/min/1.73 m², the eGFR cutoff of 120 mL/min/1.73 m² is considered unnecessary. In addition, little data is available to evaluate PK in patients with eGFR in the range of 30-60 mL/min/1.73 m². It is recommended that the dose is reduced by half for patients in this renal function category based on data from adult RA and the understanding of the elimination mechanism of baricitinib.

The analysis also confirmed body weight as a significant covariate on apparent clearance (CL/F) and apparent volume of distribution (V/F). Simulations were conducted to identify an optimal dosing regimen for patients with WT \leq 10 kg, based on a target concentration range which is defined as the 90% confidence intervals for daily average concentrations (C_{av}) at the final stable doses for all CANDLE patients who achieved disease control. The results suggested a dosing regimen of 1 mg TID as starting dose and 1 mg QID as escalated dose provided exposures better in line with the target concentration range and most comparable to the other body weight groups.

If a patient gains weight during the study and the increase in weight results in a change in weight range, the investigator may opt to increase the dose based on the patient's new weight range according to [Table JAJE.5](#) for patients with eGFR \geq 60 mL/min/1.73 m² and for patients with eGFR $<$ 60 mL/min/1.73 m². The investigator should ensure that the increase in weight is not related to fluid retention. If the patient loses weight during the study, the investigator may opt to keep the patient on their current dose.

6. Study Population

Patients enrolled into this study will have been diagnosed with an autoinflammatory disorder such as NNS/CANDLE, SAVI, or AGS.

Patients who meet all of the inclusion criteria (Section 6.1) and do not meet any of the exclusion criteria (Section 6.2) may enter the study (that is, sign consent or assent). In addition, patients must meet the enrollment criteria (Section 6.1) in order to be eligible to receive baricitinib.

Prospective approval of protocol violations to recruitment and enrollment criteria, also known as protocol waivers or exemptions, are not permitted.

6.1. Inclusion Criteria

Patients are eligible for entry into the study only if they meet all of the following criteria at Visit 1 (screening) and Visit 6 (enrollment, baseline) unless otherwise specifically defined:

Type of Patient and Disease Characteristics

- [1] Have systemic signs and symptoms of inflammation as manifested by the presence of 2 or more signs or symptoms as defined in CANDLE/SAVI/AGS diary (investigator must assess patient eligibility using a patient diary related to their disease; see Section 9.1.1.1, 9.1.1.2, and 9.1.1.3)
- [2] Have been diagnosed with NNS/CANDLE, SAVI, or AGS (including FCL) with the confirmation with genetic diagnosis.
- [3] Have the designated daily diary score assessed over the designated period during the screening and pretreatment period. Average daily diary score will be calculated using data from 7 days preceding the current visit (not including data on the day of current visit) (see Section 9.1.1.1)

Average daily diary score at Visit 2 (only for NNS/CANDLE patients) and Visit 6 (for all patients):

- NNS/CANDLE patients: average daily diary score of ≥ 0.5 ,
- SAVI patients: average daily diary score of ≥ 1.0 ,
- AGS patients: average daily diary score of ≥ 0.5 .

Note: SAVI and AGS patients are required to collect daily diary score over at least 7 days prior to Visit 6. If scores are missing and the total number of daily diary score is < 7 days, the eligibility for moving to Visit 6 may be considered after consultation with Lilly or its designee. NNS/CANDLE patients are required to collect daily diary score through 13 weeks according to the screening and pre-treatment period.

If the average daily diary score does not meet the criterion, but the patient's condition warrants appropriate assessment in this study, moving to Visit 6 may be allowed after consultation with Lilly or its designee. The eligibility for moving to Visit 6 will be judged by Lilly or its designee.

Patient Characteristics

[4] are male or female patients:

[4a] Female patients:

Women not of child-bearing potential or nonbreastfeeding:

- 12 months of amenorrhea for women >55 , with no need for FSH
OR
- 12 months of amenorrhea for women >40 years old with FSH ≥ 40 mIU/mL and no other medical condition such as anorexia nervosa and not taking medications during the amenorrhea (e.g. oral contraceptives, hormones, gonadotropin releasing hormone, anti-estrogens, selective estrogen receptor modulators (SERMs), or chemotherapy that induced amenorrhea)

OR

- Women who are congenitally or surgically sterile (ie, have had a hysterectomy or bilateral salpingectomy or bilateral oophorectomy).

Women of child-bearing potential:

- Must test negative for pregnancy prior to Visit 6 as indicated by a negative serum pregnancy test at the screening visit followed by a negative urine pregnancy test within 24 hours prior to exposure.

AND either of the following:

- Must agree to either remain abstinent, if complete abstinence is their preferred and usual lifestyle, or remain in same-sex relationships, if part of their preferred and usual lifestyle, without sexual relationships with males. Periodic abstinence (eg, calendar, ovulation, symptothermal, or post ovulation methods), declaration of abstinence just for the duration of a trial, and withdrawal are not acceptable methods of contraception.

OR

- Must agree to use a reliable method of birth control when engaging in sexual intercourse with a male partner while enrolled in the study and for at least 4 weeks following the last dose of baricitinib.

Each of the following is considered a highly effective method of birth control:

- oral contraceptives
- condom with a spermicide
- intrauterine device
- vasectomized male (with appropriate post vasectomy documentation of the absence of sperm in the ejaculate). For female patients in the

study, the vasectomized male partner should be the sole partner for that patient.

Contraceptive use by women should be consistent with local regulations regarding the methods of contraception for those participating in clinical studies.

Note: Female patients of child-bearing potential will be defined as ≥ 10 years old and have reached menarche, or if there is a reason to believe that the patient is sexually active. At the discretion of the investigator, female patients who are <10 years old may also be tested as needed.

[4b] Male patients:

Must agree to use the above highly effective birth control (see inclusion criterion 4a) while engaging in sexual intercourse with female partners of childbearing potential while enrolled in the study and for at least 4 weeks following the last dose of baricitinib.

[5] Are the following age, based on each disease type:

[5a] NNS/CANDLE and SAVI patients: Are ≥ 17.5 months of age,

[5b] AGS patients: Are ≥ 6 months of age.

[6] Are ≥ 5 kg in body weight.

Informed Consent

[7] Have the ability to provide informed consent or have a legal guardian who is willing and able to provide written informed consent, provided that assent is obtained from patients per local requirements.

Note: Full date of birth will be collected from patients <18 years old.

Note: During clinical trials, adequate informed consent for continued participation will be obtained from pediatric patients once a child reaches the age of legal consent.

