8.3. Lost to Follow-Up

A patient will be considered lost to follow-up- if he or she repeatedly fails to return for scheduled visits and is unable to be contacted by the study site. Site personnel are expected to make diligent attempts to contact patients who fail to return for a scheduled visit or were otherwise unable to be followed up by the site.

9. Study Assessments and Procedures

Study procedures and their timing are summarized in the Schedule of Activities (Section 2). Protocol waivers or exemptions are not allowed.

Immediate safety concerns should be discussed with the sponsor upon occurrence or awareness to determine if the patient should continue or discontinue study intervention.

Adherence to the study design requirements, including those specified in the Schedule of Activities, is essential and required for study conduct.

All screening evaluations must be completed and reviewed to confirm that potential patients meet all eligibility criteria. The investigator will maintain a screening log to record details of all patients screened and to confirm eligibility or record reasons for screening failure, as applicable.

[Appendix 2](#) lists the laboratory tests that will be performed for this study.

Unless otherwise stated in the subsections below, all samples collected for specified laboratory tests will be destroyed within 60 days of receipt of confirmed test results. Certain samples may be retained for a longer period, if necessary, to comply with applicable laws, regulations, or laboratory certification standards.

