**Table JAJE.3 Thresholds of reduction in patient's mean daily diary scores**

Variables	Disease	Threshold
Mean daily diary score	NNS/CANDLE	mean daily score to <0.5
	SAVI	mean daily score to <1.0
		mean daily score excluding the respiratory/breathing symptom score to <1.0
		mean daily score to <0.5
		mean daily score excluding the respiratory/breathing symptom score to <0.5
	AGS	mean daily score to <0.5
		mean daily score excluding neurological symptoms to <0.5

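### Protocol 6.1 criterion [3] leaves entry below the diary-score floor to open-ended sponsor judgement, and a patient so admitted already meets the matching full-score response cut-off at baseline

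*Protocol*

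**What the plan says.** Protocol 6.1, criterion [3], sets a floor on the seven-day average diary score at Visit 6 for all patients, and also at Visit 2 for NNS/CANDLE: "NNS/CANDLE patients: average daily diary score of ≥ 0.5", "SAVI patients: average daily diary score of ≥ 1.0", and 0.5 again for AGS. It then provides an exception under which "moving to Visit 6 may be allowed after consultation with Lilly or its designee". The patient concerned is described in these words: "If the average daily diary score does not meet the criterion, but the patient's condition warrants appropriate assessment in this study". The decision belongs to the sponsor: "The eligibility for moving to Visit 6 will be judged by Lilly or its designee".

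Protocol Section 6, just before the criteria, says that prospective approvals of departures from enrollment criteria, "also known as protocol waivers or exemptions, are not permitted". The opening of Section 9 repeats: "Protocol waivers or exemptions are not allowed".

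SAP 6.8.1 takes as the primary result the mean change from baseline in the diary score, by disease, at Week 20 (NNS/CANDLE) or Week 32 (SAVI, AGS). SAP 6.8.2 adds, by visit, the percentage of patients reaching the thresholds in Table JAJE.3. For the full score in NNS/CANDLE and AGS the row is "mean daily score to <0.5". SAVI has full-score rows at <1.0 and <0.5. No row refers to the baseline score.

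The two documents define the enrolled set differently. Protocol 10.2 requires that all eligibility criteria are met. SAP 6.3 takes everyone who entered and was not a screen failure at or before Visit 6, and its efficacy population is those patients with at least one dose.

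**The concern.** There are two linked problems. First, the entry rule for the variable that carries the primary endpoint can be set aside case by case by the sponsor. The protocol elsewhere says that enrollment criteria are not waived. Criterion [22] shows that a tighter form was available: its exception names a condition (the abnormality is attributable to the underlying disease) and requires documentation as well as consultation. Criterion [3] has only the consultation.

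Second, the floor does statistical work. It keeps out patients who already satisfy the full-score response definition and who have little room to fall. Once the floor can be passed over, the responder percentage can include a patient who never changed, and the primary mean can include one whose possible change is small. With about 5 patients over three diseases, one patient is a large share of any group. Protocol 10.3.6 and SAP 6.15 say that these summaries support a regulatory submission.

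**Working it through.** The plan gives no power, alpha or effect figure to reproduce. Enrolment is about 5 by feasibility (Protocol 10.1) and the analysis is descriptive (Protocol 10.3.3). The check is direct arithmetic.

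**1. Floor against cut-off.** Inputs: Protocol 6.1 [3] and SAP Table JAJE.3.

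| Disease | Entry floor | Matching full-score cut-off |
|---|---|---|
| NNS/CANDLE | ≥0.5 | <0.5 |
| SAVI | ≥1.0 | <1.0 |
| AGS | ≥0.5 | <0.5 |

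The two are exact complements. Baseline is normally Visit 6 (SAP 6.1.1). Every patient below the floor at Visit 6 therefore meets the matching cut-off at baseline, and no patient at or above the floor does. An NNS/CANDLE patient who missed the floor only at Visit 2 is not affected.

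**2. Room to fall.** The fall cannot exceed the baseline, so it is below 0.5 (NNS/CANDLE, AGS) or below 1.0 (SAVI). Assuming whole-number item scores and seven recorded days, the highest scores under the floor are:
- NNS/CANDLE: 17/(7×5) = 0.486
- SAVI: 41/(7×6) = 0.976
- AGS: 27/(7×8) = 0.482

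**3. Responder percentage.** Assume one below-floor patient whose score stays below the cut-off, in a group of n with r responders among the others. With the patient it is (r+1)/n; without, r/(n-1).

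| n | r | With | Without |
|---|---|---|---|
| 2 | 0 | 1/2 = 50% | 0/1 = 0% |
| 2 | 1 | 2/2 = 100% | 1/1 = 100% |
| 3 | 0 | 1/3 = 33.3% | 0/2 = 0% |
| 3 | 1 | 2/3 = 66.7% | 1/2 = 50% |
| 5 | 0 | 1/5 = 20% | 0/4 = 0% |
| 5 | 2 | 3/5 = 60% | 2/4 = 50% |

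**4. Mean change.** Let c be the mean change in the others and e the change in this patient. The group mean is ((n-1)c + e)/n. The documents give neither value, so both are assumed.
- c = -1.0, e = 0: n=2, -1.0/2 = -0.50; n=3, -2.0/3 = -0.67; n=5, -4.0/5 = -0.80. Without this patient the mean is -1.0.
- c = -0.25, e = -0.4: n=2, -0.65/2 = -0.325; n=5, -1.4/5 = -0.28. Without this patient the mean is -0.25, so there is no dilution.

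**5. Rows that are not assured.** A SAVI patient admitted at 0.5 or more but under 1.0 does not start below the <0.5 full-score row. Rows that leave out an item can also differ. A SAVI full score of 41/42 = 0.976 with a respiratory score of 0 becomes 41/35 = 1.171 without that item. An AGS full score of 27/56 = 0.482 with a neurologic disability score of 0 becomes 27/49 = 0.551 if only that item is dropped.

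**The case against.** The sponsor can say that the exception is part of criterion [3], that the lead-in to the criteria allows an individual criterion to define things differently, and that a patient admitted this way is therefore no violation. Criteria [22], [27] and [28] also use sponsor consultation, and the sentence in Section 9 stands in a passage about procedures and visit adherence. Much of this stands: a flat breach of the waiver ban might be inferred, but it is not established. What remains is that the exception itself describes a patient who does not meet the criterion, and gives no objective condition for admitting that patient.

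A reader might also take the floor to be the only safeguard. It is not: criterion [1] requires two or more diary signs or symptoms. That is weaker, however. Two items scored 1 every day average 2/5 = 0.40, 2/6 = 0.33 or 2/8 = 0.25, all below the floor.

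Nor would such a patient be invisible. SAP 6.8.3 provides by-visit listings of score and change, with spaghetti plots. SAP 6.14 lists important deviations, incorrect enrolment being one example, and leaves any analysis that excludes data to a separate plan. With about 5 patients a low baseline would be noticed. But a listing does not correct a percentage, and a sponsor-approved admission may never be classed as a deviation.

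Finally, SAP 6.8.2 speaks of reduction, which could be read as requiring some fall. No such rule is written: the table rows are defined by the score reached.

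**Conclusion.** The point holds in a limited form. The exception in criterion [3] and the ban in Section 6 need reconciling. A patient below the floor at Visit 6 meets the matching full-score cut-off before the first dose and, as the SAP is written, is counted at each later visit where the score remains below it. For SAVI this is assured only for the full-score <1.0 row. If nobody else responds, one such patient produces 50%, 33.3% or 20% in groups of 2, 3 or 5.

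Two stronger readings are not supported. One is that such a patient necessarily pulls the primary mean toward zero. The low baseline limits the fall, but dilution needs the others to improve more. That is not certain, particularly in AGS, where Protocol 3.3 reports a hypothesis that the diary was insensitive to change. Where dilution does occur, it makes the drug look less effective. The other is that results have been affected: nothing in the documents shows that anyone entered through the exception. The sizes rest on assumed changes and group sizes. It is also unclear whether such a patient belongs in the analysis set, because Protocol 10.2 and SAP 6.3 differ.

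**What to change.** In Protocol 6.1 [3], state the conditions for the exception inside the criterion and require them to be documented, so that it no longer conflicts with Section 6. Enrolment appears complete: SAP 6.15 sets the Week 52 analysis after all planned enrolled patients reach Week 52 or discontinue, and the SAP revision history places that lock in the past. The protocol edit would therefore mainly clarify the record. The SAP change is still useful, because Version 5 is to be approved before final lock.

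In SAP 6.8.1 and 6.8.2:
- state whether patients admitted below the floor are in the efficacy population;
- flag them in the listings;
- give the primary mean change with and without them;
- report each responder percentage also among patients whose baseline is at or above that row's cut-off, removing the others from both numerator and denominator.

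Removing a patient from the numerator alone would be wrong. It would force non-response even on a patient who fell from 0.4 to 0. Using each row's own baseline matters because the full-score floor does not settle where a patient starts on the rows that omit an item.

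The cost is a few sentences, smaller denominators and possibly a lower responder percentage. If no patient used the exception, one sentence saying so closes the point.
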